2.3 DETERMINATION OF SAMPLE SIZE

The main purpose of this study is hypothesis generation and estimation regarding the impact on pulmonary function in terms of the change in FVC, as measured by daily handheld spirometry, in patients suspected to suffer from IPF.

For this study, a total sample size of approximately 180 patients was planned (Table 2). The majority of the patients will be enrolled into two study cohorts, i.e., patients with a diagnosis of IPF or non-IPF ILD. Due to the uncertainty of the numbers of patients to be enrolled into these two cohorts, the sample size could not be derived for a certain patient number. For the purpose of sample size and power calculation, it was assumed that approximately 40% of patients will be diagnosed with IPF and 50% of patients will be diagnosed with non-IPF ILD. Approximately 10% of patients were expected to suffer from a disease other than ILD (non-ILD) or were expected not have a diagnosis within 12 months of enrollment. This assumption was based on published data (Wapenaar-deKorver et al. 2016).

Thus, it was expected to enroll approx. 72 patients with a diagnosis of IPF and approx. 90 patients with a diagnosis of non-IPF ILD. Approximately 18 patients may be diagnosed with non-ILD or have no diagnosis within the 12 months period following enrollment.

Table 2 Sample Size Scenarios

Number of patients with IPF	Mean FVC decline [mL] over 6 months	Lower Bound of 95% CI	Upper Bound of 95% CI	Total number of patients to be enrolled
72	25	8.83	41.17	180
72	50	33.83	66.17	180
72	75	58.83	91.17	180

CI = confidence interval

In Table 2 point estimates and 95% confidence intervals based on a normal distribution are tabulated for a range of possible outcomes, assuming 72 patients

analyzed, a standard deviation of 70 ml, and a precision of 16.17% (estimates produced using nQuery, version 7). A mean semi-annual FVC decline in the IPF group of 50 mL was considered to be a clinically relevant decline and a reasonable expectation in accordance with the literature (Ley et al. 2011). In addition, after inspection of historical data, it could be assumed that the common standard deviation in mean FVC decline was 70 mL as measured by handheld spirometry.

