4.1 ANALYSIS POPULATIONS

No analysis populations are defined in this trial. Data of all enrolled patients will be analyzed (enrolled patients have signed informed consent and passed all in- and exclusion criteria) by diagnosis cohorts, if possible.

Following thorough assessments and diagnoses, four groups of patients will be identified and allocated to one of the following diagnosis cohorts:

- Patients diagnosed with IPF (IPF patients)
- Patients diagnosed with an ILD other than IPF (non-IPF ILD patients)

F. Hoffmann-La Roche Ltd
Statistical Analysis Plan MA39297, Final Version 2.0

- Patients diagnosed with a condition that is not an ILD (non-ILD patients)
- Patients without diagnosis after 12 months assessments

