4.2 TRIAL PERIODS, OBSERVATION AND ANALYSIS TIMES

The study consists of the peri-diagnosis period (from enrollment until end of study visit), which is divided into a pre- and post-diagnosis period (please refer to Sections [4.2.3](#) and [4.2.4](#) for the definition of these periods). Site visits will be conducted at a minimum at baseline, diagnosis, and end-of-study for each individual patient. During each study period, every patient should have at least one site visit, scheduled at the discretion of the investigator.

All patients will be managed at the discretion of the Investigator taking into account local clinical practice guidelines and standards of care as well as available clinical evidence for patients with suspected IPF/ILD or diagnosed with IPF/ILD.

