4.2.5 End of Study

For individual patients, the end of the study will be as follows:

- Should no diagnosis be made 12 months after inclusion into the study, the patient will leave the study and perform the end of study visit
- Patients diagnosed with a non-ILD condition will leave the study on the date of diagnosis

- Patients diagnosed with IPF or non-IPF ILD will remain in the study and be followed up to the start of drug treatment (within six months) or a maximum of six months if no drug treatment is prescribed

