4.7 SAFETY ANALYSES

4.7.1 Safety Endpoints

The following safety endpoints will be analyzed descriptively by diagnosis cohorts:

- **Non-elective hospitalization, both respiratory and all cause:** a listing and a frequency table will be provided displaying number of patients with at least one non-elective hospitalization, the number of non-elective hospitalizations, the number of patients with at least one respiratory-related non-elective

hospitalization and the number of respiratory-related non-elective hospitalizations during pre- or post-diagnosis periods by diagnosis cohorts.

- **Investigator-reported acute exacerbations:** a listing and a frequency table will be provided displaying number of patients with at least one acute exacerbation and number of acute exacerbations during pre- and post-diagnosis periods by diagnosis cohorts. Additionally, number of patients and events will be given separately for triggered and idiopathic acute exacerbations. Acute exacerbation are defined as per Collard et al. 2016: answering No to the eCRF question “Is there an extra-parenchymal cause identified?”; and answering Yes to the eCRF question “Are there new, bilateral GGO (Ground glass opacification)/ consolidation on CT?” Please refer to [Appendix 8](#) for further information.
- **Death, all cause and respiratory-related:** a listing and a frequency table is given including number of deaths during pre- and post-diagnosis period, primary cause of death and frequencies with respect to autopsies performed.
- **Events related to the study assessments:** documented events will be coded with MedDRA version 21.1 or a higher one. Frequencies of events will be displayed by System Organ Class (SOC) and Preferred Terms (PT) by diagnosis cohorts. In addition, summary of the events characteristics, events by intensity and leading to study discontinuation will be presented separately. The tables will be provided for events occurring during the peri-diagnosis period. If the start date of an event is after or on the day of the enrollment visit or it is ongoing at enrollment visit and the end date of the event is after the day of the initial diagnosis visit, the event belongs to the peri-diagnosis period. A listing with all events will be also presented.

If for any of the above mentioned events an incidence rate of more than 15% is observed, time to event analyses according to the method of Kaplan-Meier will additionally be provided.

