4.8 MISSING DATA

In general, missing data will not be imputed. Exceptions will be made for events related to study assessments and concomitant medications. Here, missing start or end dates will only be imputed for the determination of whether the event or medication is allocated to the pre-, post- or peri-diagnosis period or whether the medication is considered as previous, concomitant or post medication as defined in section [4.7.3](#).

For events related to study assessments it is not expected that in case of partially missing dates only the year is given. In case the start/end day of the event is missing it will be imputed with the first/last day of the respective month assuring that the start/end date is after the day of the enrollment visit. In case the date is completely missing, it will be assumed that the event occurred during peri-diagnosis period.

If the medication start date is partially missing the day and month will be imputed with the earliest possible date but not prior to the date of enrollment. If the medication end date is partially missing the day and month will be imputed with the latest possible date not after death or end of study (i.e. DEC for month and 28/29/30/31 for day). In case the start/end date of a medication is completely missing, it will not be imputed and the medication will be considered a concomitant medication.

F. Hoffmann-La Roche Ltd
Statistical Analysis Plan MA39297, Final Version 2.0

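### The rule in SAP 4.7.1 for placing study-assessment events in the peri-diagnosis period conflicts with the period in 4.2, and its unbracketed wording leaves open how many events the tables lose

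*SAP*

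**What the plan says.** Section 4.7.1 of the SAP limits the summaries of events related to study assessments to one period: "The tables will be provided for events occurring during the peri-diagnosis period". These summaries cover frequencies by SOC and PT, event characteristics, intensity, and events leading to discontinuation.

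The rule for membership is a single sentence. It opens with two alternatives, "If the start date of an event is after or on the day of the enrollment visit or it is ongoing at enrollment visit", and then adds, joined by a bare 'and', that "the end date of the event is after the day of the initial diagnosis visit". No brackets or punctuation show whether the last condition governs both alternatives or only the second.

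Section 4.2 defines the period differently: "The study consists of the peri-diagnosis period (from enrollment until end of study visit", divided there into a pre- and a post-diagnosis part. Section 2.2 agrees that the period covers both parts.

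Four other statements bear on the rule:

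- Section 4.1 lists four diagnosis cohorts, one of them "Patients without diagnosis after 12 months assessments". Section 4.7.1 asks for the safety summaries by diagnosis cohort.
- Section 4.2.5 states: "Patients diagnosed with a non-ILD condition will leave the study on the date of diagnosis".
- Section 2.3 gives the expected numbers: "Approximately 18 patients may be diagnosed with non-ILD or have no diagnosis within the 12 months period following enrollment".
- Section 4.8 states, for these events: "In case the date is completely missing, it will be assumed that the event occurred during peri-diagnosis period".

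**The concern.** The peri-diagnosis period starts at enrollment and contains the whole pre-diagnosis period. An event that starts and resolves between enrollment and diagnosis lies wholly inside it. A condition on the end date relative to diagnosis can therefore only remove events that belong. It also refers to a visit that one of the four cohorts never has.

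These are the only planned frequency tables for events caused by the study procedures, and the study has no investigational product. The pre-diagnosis period may last up to 12 of a maximum of 18 months, so the part of follow-up at risk of being left out is not small. Two programmers could also follow the sentence faithfully and deliver different tables. A low count could in turn keep the observed incidence below the 15% at which section 4.7.1 adds a Kaplan-Meier analysis.

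**Working it through.** The SAP gives no figure to reproduce here. The check is logical, with an illustrative date grid.

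**Conditions (section 4.7.1)**

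- A: the event starts on or after the enrollment visit.
- B: the event is ongoing at the enrollment visit.
- C: the event ends after the initial diagnosis visit.

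**Two groupings**

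- Reading 1: (A or B) and C.
- Reading 2: A or (B and C).

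**Reference (section 4.2):** the event overlaps the time from enrollment to the end of study visit. C plays no part.

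**Single cases**, in days from enrollment, with diagnosis at day 180 where there is one:

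| Event | Reading 1 | Reading 2 | Section 4.2 |
|---|---|---|---|
| Day 20 to 25, diagnosed | out | in | in |
| Day 20 to 25, never diagnosed | out | in | in |
| Day 175 to 180, diagnosed | out | in | in |
| Day 170 to 200, diagnosed | in | in | in |
| Day -5 to 10, diagnosed | out | out | in |
| Day -5 to 10, never diagnosed | out | out | in |

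**Grid.** Assumptions: enrollment is day 0; starts are every 5 days from day -30 to the end of study; durations are 0, 1, 7, 30 and 90 days; events that end before enrollment are left out. C counts as not met when there is no diagnosis visit.

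| Cohort (assumed dates) | Section 4.2 | Reading 1 keeps | Reading 2 keeps |
|---|---|---|---|
| IPF or non-IPF ILD (diagnosis day 180, end day 360) | 378 | 207 | 365 |
| Non-ILD (diagnosis and end day 180) | 198 | 27 | 185 |
| Undiagnosed (end day 365) | 383 | 0 | 370 |

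Reading 1 drops 378 - 207 = 171, 198 - 27 = 171, and 383 - 0 = 383 patterns. Reading 2 drops 378 - 365 = 13, 198 - 185 = 13, and 383 - 370 = 13. Those 13 are the same patterns each time: the ones that start before enrollment and are still running at it. In the non-ILD row, the 27 patterns kept under Reading 1 are those that continue after the patient has left.

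These are counts of date patterns. They show which kinds of event each reading loses and do not forecast numbers of events.

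**Cohort size.** Non-ILD and undiagnosed patients combined: 10% of 180 = 18. The SAP does not split the 18.

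**Check against section 4.8.** Under Reading 1, an event with no dates at all is counted as peri-diagnosis, while a fully dated event from day 20 to day 25 is not. Better information would remove the event from the table.

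**The case against.** The strongest reply is that Reading 2 is meant. By ordinary precedence 'and' binds before 'or', so a start on or after enrollment is enough by itself. The medication rule in section 4.7.3 points the same way: it identifies use during the peri-diagnosis period from the enrollment visit alone, with no reference to diagnosis. Section 4.8 speaks of allocating events to the pre-, post- or peri-diagnosis period, which would be odd if events resolved before diagnosis were meant to be left out.

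On that reading the loss is close to nil. Events caused by study assessments should rarely be under way at enrollment: the study kit is issued upon enrollment, and the schedule in Appendix 2 marks no collection of these events at that visit.

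Much of this stands. A reader might infer that the plan certainly discards every event resolved before diagnosis and every event of undiagnosed patients. The document does not support that as a fact; it follows from Reading 1 only, and the parallel medication rule favors Reading 2. Nor should the 18 patients be read as all undiagnosed or all non-ILD.

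The reply does not remove the defect. The sentence nowhere says which grouping applies, and Reading 2 still excludes events that section 4.2 includes.

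A second reply is that section 4.5 confines peri-diagnosis analyses to IPF and non-IPF ILD patients. That statement sits in the efficacy section and concerns daily measurements, whereas section 4.7.1 asks for tables by diagnosis cohort. Even if it applied, Reading 1 would still drop the resolved pre-diagnosis events of IPF and non-IPF ILD patients.

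**Conclusion.** The point holds: section 4.7.1 states a membership rule that contradicts the period defined in section 4.2 under either grouping, and the grouping itself is not fixed.

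- Under Reading 1 the loss is large: every event resolved by diagnosis, every event of undiagnosed patients, and all non-ILD events except those that outlast the patient's participation.
- Under Reading 2 it should be small: only events ongoing at enrollment that end by diagnosis, or that have no diagnosis visit.

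This assumes that the end-date condition fails when there is no diagnosis visit. The document gives no event rates, so the number of events affected cannot be stated.

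The consequence is bounded. Section 4.7.1 also provides a listing of all events, so a reader should not infer that any event leaves the report. The rule is stated for study-assessment events only, not for hospitalizations, acute exacerbations or deaths. The tables are descriptive and the primary endpoint is untouched. What could be wrong is the frequency tables and the decision on the 15% trigger. The rule should be corrected before the final tables are programmed.

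**What to change.** Delete the end-date condition from section 4.7.1. State instead that an event related to study assessments belongs to the peri-diagnosis period if it starts on or after the enrollment visit and no later than the end of study visit, or if it is ongoing at the enrollment visit. Add that this applies to all diagnosis cohorts, including patients without a diagnosis.

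No pre/post split of these events is needed, since section 4.7.1 does not plan one. The separate exclusion in section 4.2.4 of data collected after treatment start is not changed by this.

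The cost is one sentence in the SAP and one date flag in the programming. No new data are required.

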4.7.2 Vital Signs

A summary table displaying vital signs values (heart rate, systolic and diastolic blood pressure) by visit and changes from baseline will be provided by diagnosis cohorts. In case more than one visit was performed during the pre- and post-diagnosis period, mean parameter values of these visits will be used for the derivation of descriptive statistics.

4.7.3 Previous and Concomitant Medication

Previous and concomitant medications will be coded using the Genentech (GNE) drug dictionary. This is a proprietary Roche Dictionary which is used to code concomitant

F. Hoffmann-La Roche Ltd
Statistical Analysis Plan MA39297, Final Version 2.0

medications in the Trial Management System (TMS) coding tool. The Standardized Medication Name (CMDECOD), which is the medication generic or combination generic as defined by the Drug Thesaurus (proprietary Genentech/Roche dictionary), and the Medication Class (CMCLAS), which is the primary medication class as defined by the Drug Thesaurus, will be used for the analyses

Medications will be classified as previous, concomitant or post as follows:

Previous: If the medication end date is prior to the day of the enrollment visit.

Concomitant: If medication start date is on or after the day of the enrollment visit or if the medication start date is prior to the day of the enrollment visit but ongoing at the day of the enrollment visit, i.e. is taken during the peri-diagnosis period.

Post: if the medications start date occurred after the diagnosis date, i.e. the medication started in post-diagnosis period.

The number and frequencies of patients taking previous, concomitant and post medications will be presented by Medication Class and Standardized Medication Name. If patients receive more than one drug within a Medication Class or Standardized Medication Name they will be counted only once for the respective Medication Class or Standardized Medication Name.

4.8 MISSING DATA

In general, missing data will not be imputed. Exceptions will be made for events related to study assessments and concomitant medications. Here, missing start or end dates will only be imputed for the determination of whether the event or medication is allocated to the pre-, post- or peri-diagnosis period or whether the medication is considered as previous, concomitant or post medication as defined in section [4.7.3](#).

For events related to study assessments it is not expected that in case of partially missing dates only the year is given. In case the start/end day of the event is missing it will be imputed with the first/last day of the respective month assuring that the start/end date is after the day of the enrollment visit. In case the date is completely missing, it will be assumed that the event occurred during peri-diagnosis period.

If the medication start date is partially missing the day and month will be imputed with the earliest possible date but not prior to the date of enrollment. If the medication end date is partially missing the day and month will be imputed with the latest possible date not after death or end of study (i.e. DEC for month and 28/29/30/31 for day). In case the start/end date of a medication is completely missing, it will not be imputed and the medication will be considered a concomitant medication.

F. Hoffmann-La Roche Ltd
Statistical Analysis Plan MA39297, Final Version 2.0

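### The enrollment floor on partial medication start dates ignores the recorded year and the stop date, so a drug stopped before enrollment can be listed as both previous and concomitant

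*SAP*

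**What the plan says.** Section 4.8 (Missing Data) has three rules for medication dates:

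- A partially missing start has its day and month "imputed with the earliest possible date but not prior to the date of enrollment".
- A partially missing end is "imputed with the latest possible date not after death or end of study".
- If the start/end date is completely missing, "it will not be imputed and the medication will be considered a concomitant medication".

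These dates are imputed only to settle the study period and "whether the medication is considered as previous, concomitant or post medication as defined in section" 4.7.3.

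Section 4.7.3 defines the classes that matter here:

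- The previous class looks only at when the drug stopped: "Previous: If the medication end date is prior to the day of the enrollment visit".
- The concomitant class has two limbs. The first looks only at when the drug began: "If medication start date is on or after the day of the enrollment visit". The second catches drugs already in use at entry: "medication start date is prior to the day of the enrollment visit but ongoing at the day of the enrollment visit". A closing gloss explains that the drug is taken in the peri-diagnosis period.

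The section does not say that the classes exclude each other, gives no order of precedence, and does not require the start to be on or before the stop. Counts of patients are then tabulated for each class.

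**The concern.** The floor stops an imputed start from falling before enrollment, but a partial start date often belongs to a drug that did begin before enrollment. If such a drug had also stopped by then, the imputed start lies after its own stop. The two definitions read different dates, so one record can satisfy both.

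The medication tables describe what patients took while they were observed untreated for their lung disease. A drug stopped before enrollment should not appear in the concomitant table. The amendment rationale for version 2 says that the missing-data rules no longer use the prior flag from the eCRF and rely on the dates, so nothing else in the rule corrects the class.

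**Working it through.** The plan gives no figure to reproduce here, so the check applies the two sections literally to test records.

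**Inputs.** Assumed dates: enrollment 15 Mar 2018, diagnosis 1 Sep 2018, end of study 1 Feb 2019. The enrollment date fits the SAP's own timeline: first patient expected in Q3 2017 (Appendix 1, Length of Study) and enrollment complete in February 2019 (section 4.9).

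**Rules as coded.**
- Imputed start = the later of (first day of the recorded year or month) and (enrollment date).
- Imputed end = the earlier of (last day of the recorded year or month) and (end of study).
- Previous if end < enrollment.
- Concomitant if start ≥ enrollment, or if start < enrollment and the drug is ongoing at enrollment.

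| Recorded start | Recorded stop | Imputed start | Stop used | Class as written | Class without the floor |
|---|---|---|---|---|---|
| 2018 | 20 Feb 2018 | 15 Mar 2018 | 20 Feb 2018 | Previous and Concomitant | Previous |
| 2015 | 10 Jun 2016 | 15 Mar 2018 | 10 Jun 2016 | Previous and Concomitant | Previous |
| Apr 2015 | 2016 | 15 Mar 2018 | 31 Dec 2016 | Previous and Concomitant | Previous |
| 5 Apr 2015 (full date) | 10 Jun 2016 | none needed | 10 Jun 2016 | Previous | Previous |
| 2015 | ongoing | 15 Mar 2018 | none | Concomitant | Concomitant |
| 2018 | ongoing | 15 Mar 2018 | none | Concomitant | Concomitant |
| 2018 | 2018 | 15 Mar 2018 | 31 Dec 2018 | Concomitant | Concomitant |

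**Row 1** does not depend on how the year is treated. The later of 1 Jan 2018 and 15 Mar 2018 is 15 Mar 2018, which is 8 + 15 = 23 days after the stop. The stop is before enrollment, so the drug is previous. The start is on enrollment day, so it is also concomitant.

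**Rows 2 and 3** use the reading in which the floor overrides the recorded year. The sentence names only day and month as imputed. If the year is kept, the candidates for row 2 run from 1 Jan to 31 Dec 2015 and none reaches 15 Mar 2018, so the instruction cannot be carried out. The text does not say which reading applies.

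**What the floor achieves.** In these records it changes the class only for drugs stopped before enrollment, and there it adds a wrong class. Drugs still in use at enrollment are concomitant through the second limb anyway.

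**Completely missing start.** This was reasoned from the text, not run. With no start and a stop on 10 Jun 2016, section 4.7.3 gives previous, because that class needs only the stop. If the slash in section 4.8 means that either date is missing, section 4.8 gives concomitant. If it means both, there is no conflict.

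**The case against.** The strongest reply is that section 4.8 imputes the day and month, not the year. On that reading a start recorded as '2015' becomes 1 Jan 2015, and the floor acts only when enrollment falls inside the recorded period. This is a sensible reading and may be what was meant, but the sentence attaches the floor without that condition. It also does not help row 1, where enrollment does fall inside the recorded year.

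Second, the gloss in section 4.7.3 about use in the peri-diagnosis period could be read as governing both limbs, which would exclude a drug stopped earlier. It shows the intent. It does not remove the imputed start that meets the first limb, and it sets no precedence. A programmer who gave the previous class priority would avoid the double listing, but the SAP does not ask for that.

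Third, few records may be affected. Footnote j of the schedule in Appendix 2 describes concomitant medications as those used from inclusion onward. This stands as a limit on size. A table of previous medications is still planned, so some earlier drugs are expected in the data.

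A reader might go further and infer that every drug with a partial or missing start and an earlier stop is misclassified, or that past lung treatments will inflate the concomitant table. The documents do not support either. An affected drug still appears under previous, so it is listed twice rather than lost. If the recorded year is kept, drugs from earlier years need not be affected. Nothing in the SAP shows which drugs carry partial dates.

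**Conclusion.** The point holds in a narrow form. For a partial start date that includes enrollment, with a stop before enrollment, the stated rule yields a start after the stop and two incompatible classes. For a recorded year before enrollment, the rule is either unworkable or overrides known information, depending on the reading. The default for completely missing dates conflicts with section 4.7.3 only if the slash means either date.

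The consequence is minor: double listing in descriptive medication tables and listings. The primary FVC analysis is untouched, since exclusion of data after treatment start uses the treatment start date (sections 2.2.1 and 4.2.4), not the medication class. The SAP gives no count of partial dates, so the number of records cannot be estimated. The calendar dates in the example are assumed. The result needs only that the stop precedes enrollment and that both fall within the recorded year or month of the start.

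**What to change.** Reword section 4.8 so that:

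- a partial start takes the earliest date compatible with the recorded year and month;
- the enrollment floor applies only when the recorded partial date includes enrollment and the stop is not before enrollment;
- no imputed start falls after the stop;
- any drug whose stop is known to be before enrollment is previous only, whatever its start;
- the concomitant default stays for drugs whose dates do not show a stop before enrollment.

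Limiting the floor to partial dates that include enrollment is not enough alone. It resolves rows 2 and 3 of the table but leaves row 1 in both classes, so the condition on the stop is needed. With it, row 1 runs from 1 Jan to 20 Feb 2018 and is previous only, while drugs ongoing at enrollment stay concomitant.

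The cost is about two sentences in section 4.8 and a small change to the derivation of the class. No further data are needed.
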